Approximately 22,000 STEC infections occur in Canada annually at a cost of \$404 million.¹ The effects of an *E. coli* O157 infection (O157 is the most common and virulent STEC pathogen) range from asymptomatic to lethal with ~15% of infected children developing HUS 5 to 13 days after diarrhea onset.¹ HUS is defined as the presence of azotemia, thrombocytopenia and anemia. In a recent study of 770 children with HUS, 57% of children required dialysis, 93% received transfusions, and 3% died.² Among HUS survivors, 12% develop end-stage renal disease³ and in children with prolonged anuria, 100% suffer from chronic kidney disease.⁴ Currently, most STEC infections are diagnosed microbiologically several days after they present for care when they suffer from bloody diarrhea. Because of the time lag to diagnosis as well as development of HUS, monitoring of renal and hematologic parameters is recommended to enable the early identification of children who are developing HUS. Our team has recently quantified this time lag in Alberta's children (Appendix 1).⁵ We have also published guidelines that have been distributed by Alberta Health Services indicating the importance of repeating the blood tests until the HUS window has passed and of the importance of preventing dehydration (<http://www.albertahealthservices.ca/assets/info/hp/diseases/if-hp-dis-ecoli-stec.pdf>).

The prevention of dehydration in children with STEC infection is gaining prominence due to recent publications that associate early intravascular volume expansion with improved outcomes.⁶⁻⁹ It is important to note that **no therapy has been proven to prevent HUS¹⁰ or reduce kidney injury severity after HUS is established.**¹¹ To address this gap experts recommend the administration of intravascular volume expansion to all children with bloody diarrhea while awaiting culture results.¹² The rationale for this approach builds on evidence that **in children with HUS, volume expansion may improve outcomes^{6,7,9} and that dehydration and hemoconcentration are associated with adverse outcomes^{2,8,13-15} including death (OR=5.1; 95% CI 1.5, 17.6).**¹⁶ Therefore, the ability to rapidly and reliably identify children with STEC infection, and to identify other pathogens with alternative treatment, public health, and follow-up implications, has the potential to dramatically improve the care of children with hematochezia.

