1. If use of the **BioFire FilmArray**, a rapid, multi-analyte enteric pathogen detection device, reduces resource utilization in a pediatric ED when employed on children with bloody diarrhea. **We hypothesize that use of the test combined with behavioural changes by physicians will reduce the use of baseline blood tests, the administration of intravenous fluids and future health-care resource use** (children are often brought back for repeat blood tests and fluids while awaiting culture results).
2. If satisfaction is higher in individuals randomized to testing with the BioFire FilmArray arm compared with children in the standard care arm.

Potential child health improvements:

1. **Children with STEC infection will be rapidly identified:** We have shown that in the 2014 STEC outbreak in Alberta, the median time from initial health care presentation to stool sample collection was 7 hours (IQR 2, 28) and to sample receipt at the laboratory was 33 hours (IQR 18, 42). Even more concerning is that the time from initial health care encounter to positive culture was 120 (IQR 86, 205) hours. By collecting rectal swabs at the point of care we will initiate specimen processing an average of 30 hours earlier. By employing the BioFire FilmArray we will reduce stool processing time by over 80 hours.
2. **Children with STEC infection will have dehydration reversed rapidly and they will be closely monitored:** Following the rapid identification of children with STEC infection, all such children will be managed in accordance with a protocol developed by the APPETITE team for Alberta Health Services (<http://www.albertahealthservices.ca/assets/info/hp/diseases/if-hp-dis-ecoli-stec.pdf>), which includes the performance and monitoring of serum biochemistry and hematologic profiles and the prevention of dehydration. It is believed that the early administration of intravascular volume expansion has the potential to reduce the morbidity of HUS in affected children.^{6,7}

Ethics ID: REB17-1916

Title: Improvements Through the Use of a Rapid Multiplex PCR Enteric Pathogen Detection Kit in Children with Hematochezia

PI: [name]

Version 5.0 – May 16, 2018

Previous REB Approved Version Date: January 12, 2018

Page 6 of 19

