3. **Children who do not have STEC infection will avoid unnecessary blood tests, intravenous fluids and repeat visits:** As ~10% of eligible children will have STEC infection,^{25,26} the routine performance of blood tests, administration of intravascular hydration, and frequent monitoring is unnecessary in the vast majority of children with hematochezia. As such, knowledge that a result will be rapidly available will enable clinicians to confidently discharge children without performing unnecessary procedures. Those who test positive can be recalled to the ED for the appropriate management.
4. **Children will have alternative etiologies identified rapidly:** The BioFire FilmArray will also enable the rapid identification of other pathogens, some of which will require immediate therapy such as *Shigella sp.*, *Clostridium difficile*, and others that have public health implications such as *Salmonella sp.*, and norovirus.
5. **Children who do not have infectious gastroenteritis will be rapidly identified:** Children with a negative BioFire FilmArray will also be identified. This would raise the suspicion for alternative etiologies.
6. **Transmission will be reduced:** The rapid identification of infected children has the potential to reduce spread, which is common and occurs early in the course of disease. Transmission might be reduced by separating infected index cases from their at risk siblings.²⁷

3 Study Objectives

The rapid identification of STEC-infected children will enable the provision of appropriate and timely care to such children. The rapid identification of other enteric pathogens (bacteria, virus, parasite) will enable the provision of targeted therapies as appropriate and the withholding of avoidable interventions. It will also provide information for clinicians to consider alternate, non-infectious etiologies as appropriate. We hypothesize that the **BioFire FilmArray can be used selectively in children with hematochezia to identify children with STEC infection and therefore will expeditiously identify children in need of therapeutic interventions and those for whom blood testing, intravenous fluids, and follow-up visits are unnecessary.**

Knowledge of the etiology early in the course of disease will enhance the provision of a patient-level precision medicine approach to what is otherwise an ill-defined symptom.

Research Questions

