1. Do individuals randomized to testing with the BioFire FilmArray undergo fewer procedures (i.e. blood tests, intravenous fluids) and repeat healthcare visits compared with children in the standard care arm?
2. Are patient and caregiver satisfaction higher in individuals randomized to testing with the BioFire FilmArray arm compared with children in the standard care arm?

Ethics ID: REB17-1916

Title: Improvements Through the Use of a Rapid Multiplex PCR Enteric Pathogen Detection Kit in Children with Hematochezia

PI: [name]

Version 5.0 – May 16, 2018

Previous REB Approved Version Date: January 12, 2018

Page 7 of 19

Primary Objective

1. To determine if **use of the BioFire FilmArray in children with hematochezia results in a reduction in resource utilization.** Primary outcome – any blood tests (dichotomous with sub-analysis by specific blood tests); secondary – intravenous fluid administration, ED encounters.

Secondary Objectives

1. To quantify clinical outcomes – development of HUS, acute kidney injury, need for renal replacement therapy, turnaround time from BioFire result relative to stool culture result.
2. To determine if use of the BioFire FilmArray is associated with greater family satisfaction with care.
3. To determine testing criteria to optimize the clinical improvement emerging from use of the BioFire FilmArray (i.e. predictors of bacterial etiology).

4 Patients and Methods

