4.1 Study Design

We will prospectively identify children who present with hematochezia. Potentially eligible subjects will be identified by our Pediatric Emergency Medicine Research Associate Program (PEMRAP) and the Pediatric Emergency Research Team (PERT) nurses (ED coverage 14 hours per day). Eligible children will have ≥ 3 episodes of diarrhea within the preceding 24 hours and will have had blood identified in the stool (by physician, nurse or parent). Eligible subjects will be approached by a PERT team member to obtain consent (and assent when appropriate). Once consent has been obtained, study participants will be randomized by a REDCap randomization tool to ensure allocation concealment (i.e. research team, ED physicians will be unaware until after enrolled into the study and randomized). In order to optimize participants who have consented/assented to be contacted in the future regarding additional research studies as well as follow up, we will collect the following information at the initial point of contact: home, cell, work and alternate telephone numbers as well as e-mail address.

Children randomized to the standard of care arm will have demographic and clinical information collected and the treating physician will be informed to proceed as per their usual practice and treatment patterns. If stool is unavailable a rectal swab will be collected and sent to Calgary Laboratory Services (CLS) for routine culture. A routine stool specimen for back-up culture will still be requested as per standard of care. Home stool collection will be performed for those unable to provide a sample at enrolment and will be achieved by providing families with collection kits. Following the completion of the visit, data regarding all testing, procedures, and medications administered will be collected. The family will be contacted 14 days later to collect outcome information (clinical and health resource use) and satisfaction. The medical

Ethics ID: REB17-1916

Title: Improvements Through the Use of a Rapid Multiplex PCR Enteric Pathogen Detection Kit in Children with Hematochezia

PI: [name]

Version 5.0 – May 16, 2018

Previous REB Approved Version Date: January 12, 2018

Page 8 of 19

records and select administrative databases may be reviewed to ascertain and confirm outcome data on Day 28.

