4.4.2 Statistical Methods

All analyses will be undertaken by the intention-to-treat (ITT) principle. Patients who drop out or crossover will be followed and included in the ITT analysis. All statistical tests will be two-sided. Baseline characteristics will be analyzed and compared. Sensitivity analyses will be performed to assess the possibility and consequences of non-random loss to follow-up. The proportion of children who have any blood testing performed within 72 hours of randomization, **the primary outcome**, will be analyzed by comparing proportions utilizing a Fisher’s Exact test. We will use an alpha level of 0.05 for statistical testing.

The overall significance level for statistical tests on the **secondary outcomes** will be set at 0.05 with adjustment for multiple comparisons performed using a Bonferroni correction.

Ethics ID: REB17-1916

Title: Improvements Through the Use of a Rapid Multiplex PCR Enteric Pathogen Detection Kit in Children with Hematochezia

PI: [name]

Version 5.0 – May 16, 2018

Previous REB Approved Version Date: January 12, 2018

Dichotomous outcomes to be evaluated include 1) intravenous rehydration, 2) ED revisits, 3) any healthcare revisits and 4) hospitalization within the subsequent 14 days. Clinical outcomes will also include development of 5) HUS, 6) Kidney Disease Improving Global Outcomes Stage 2 or 3 creatinine based acute kidney injury,³¹ 7) antibiotic use, and 8) diagnostic imaging.

Recursive partitioning analysis will be employed to identify clinical features that select candidates for BioFire testing that maximize specificity and sensitivity to identify STEC patients. Analyses will be performed blinded to allocation assignment.

5 Adverse Event Reporting

Anticipated disease outcomes (listed below) are sought to be a natural continuation of the disease and as a result, the following will not be reported to REB:

1. IV insertion
2. Blood tests
3. Abdominal pain
4. Fever
5. Vomiting
6. Diarrhea
7. Bloody stool
8. Dialysis
9. Renal abnormalities
10. Hematological abnormalities
11. Biochemical abnormalities
12. Transfusions
13. Seizures
14. Hospital admissions
15. Other known complications of STEC infection

6 Data Handling and Record Keeping

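### Creatinine-based AKI, and to a lesser degree HUS, is compared between arms although the intervention is meant to change who has blood drawn, so detection can depend on allocation

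*Combined protocol and SAP*

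**What the plan says.** Section 4.4.2 follows its Bonferroni rule for secondary outcomes with a numbered list that includes HUS and "6) Kidney Disease Improving Global Outcomes Stage 2 or 3 creatinine based acute kidney injury". Section 1 states that "HUS is defined as the presence of azotemia, thrombocytopenia and anemia", so HUS also rests on blood results. Section 4.1.1 says that the listed outcomes will be tracked on all participants, and assigns both HUS and AKI to chart review.

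Section 3 frames "development of HUS, acute kidney injury, need for renal replacement therapy" as outcomes to quantify, but section 8 says that outcomes will be compared between the randomized groups.

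The specimens in section 4.3 are stool or a rectal swab. In the control arm "the treating physician will be informed to proceed as per their usual practice and treatment patterns"; in the BioFire arm decisions rest with the ED physician who receives the result (section 4.1). Section 4.4.1 expects 60% of controls and 20% of BioFire children to have any blood test within 72 hours.

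For STEC-positive children, section 2 points to a regional management protocol, "which includes the performance and monitoring of serum biochemistry and hematologic profiles and the prevention of dehydration", and adds: "Those who test positive can be recalled to the ED for the appropriate management".

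**The concern.** A creatinine-based outcome can be recorded only in a child whose creatinine is measured. The primary outcome is whether blood is drawn at all, so an intervention that works as intended also changes who can be found to have AKI.

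Two forces act in opposite directions. Fewer tests in STEC-negative BioFire children could leave AKI undetected in that arm. Earlier identification, monitoring and recall of STEC-positive BioFire children could raise detection there.

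The plan's safeguards address other problems. Intention-to-treat analysis and the sensitivity analysis in section 4.4.2 concern dropout, crossover and loss to follow-up. Blinded analysis does not equalize testing. For AKI, nothing says whether a child who is followed but never tested is event-free or unmeasured.

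What is at stake is the renal safety reading. Section 8 makes adoption into standard care conditional on the test being safe and effective, and section 5 exempts dialysis and renal abnormalities from ethics board reporting. A lower AKI count in the arm with fewer creatinines could be taken as reassurance when it reflects fewer measurements.

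**Working it through.** **Inputs from the documents.** Any blood test within 72 hours: 60% control, 20% BioFire; 54 children, 60 after allowing for 10% loss (section 4.4.1). STEC in about 10% of eligible children (section 2). For *E. coli* O157, about "15% of infected children developing HUS 5 to 13 days after diarrhea onset" (section 1).

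**Assumptions.** 1:1 allocation (the ratio is not stated; the budget covers 30 tests). True AKI risk equal in both arms, tried from 2% to 30%, because the documents give none. The 60% and 20% stand in for creatinine coverage, although they refer to any blood test within 72 hours.

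**1. The plan's own figure.** Exact power of a two-sided Fisher test for 60% v 20% is 80.2% at 27 per arm and 79.9% at 26, so N = 54; 54/0.9 = 60. The sample size reproduces and is not in question.

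**2. Detection ratio.** Detected AKI = true risk × P(creatinine measured | AKI). With equal true risk and untested children counted as negative, the risk cancels, leaving the ratio of the testing probabilities (BioFire:control):
- Testing unrelated to AKI: 0.20/0.60 = 0.33.
- The same, with half of the untested in each arm tested later: (0.20 + 0.80 × 0.5)/(0.60 + 0.40 × 0.5) = 0.60/0.80 = 0.75.
- Every AKI case tested in both arms because the child is ill: 1.0.
- Every AKI case tested in the BioFire arm but 60% of cases in controls: 1.00/0.60 = 1.67. The direction reverses.

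**3. If AKI is rare.** Independent binomials, 27 per arm, true risk 2%, detection 60% v 20%: the BioFire count is lower with probability 25.4% and higher with probability 7.5%. Among unequal counts, BioFire is lower in 25.4/(25.4 + 7.5) = 77%. With full and equal detection the two probabilities are 27.7% each, so 50%. Ties become common, but the tilt remains.

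**4. Chance of a significant result from unequal detection alone.** Fisher's test (named in section 4.4.2 only for the primary outcome), 27 per arm, detection 60% v 20%: p<0.05 in 0.27% of trials at 10% risk, 3.7% at 20% and 11.1% at 30%. At the Bonferroni level 0.05/8 = 0.00625, the figure at 20% risk is 0.41%.

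**5. HUS.** Expected cases in the whole trial, applying the O157 risk to all STEC: 60 × 0.10 × 0.15 = 0.9.

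**6. Why a rate among tested children is no remedy.** Take a true risk of 5%, random testing in controls, and all BioFire cases among the 20% tested. The rate among tested children is 5% in controls and 0.05/0.20 = 25% in the BioFire arm.

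**The case against.** The plan has more ascertainment than a quick reading suggests. All participants are to be tracked (section 4.1.1). Families are asked at Day 14 about visits, testing and procedures, and their report is source documentation for care outside the enrolling hospital (section 4.3). The Day 28 review collects investigations and complications, and its optional wording can be read as permission to access records. Control STEC cases are found by culture, although in the 2014 outbreak "the time from initial health care encounter to positive culture was 120 (IQR 86, 205) hours". Children ill with AKI or HUS are likely to be tested in either arm, and HUS arises days after the 72-hour window. For HUS, identification by chart review implies that an unidentified child counts as no event. Section 3 speaks only of quantifying these outcomes.

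Most of this stands, and it narrows the likely gap, more for HUS than for AKI. It does not close it: follow-up and record review can locate tests that were done but cannot supply a creatinine never drawn. The optional Day 28 wording also sits uneasily with the commitment to track everyone.

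A reader might infer a three-fold undercount of AKI in the BioFire arm. The documents do not support that: 0.33 requires testing unrelated to illness and no later testing, and the direction can reverse. A reader might equally infer that the problem disappears if AKI is rare. It does not; unequal counts become uncommon, but those that occur still tilt.

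**Conclusion.** The concern holds as a minor point of analysis and interpretation. Detection of creatinine-based AKI, and less so of HUS, can depend on allocation, and the plan would not report the coverage needed to tell whether it did.

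The size is illustrative: a detection ratio from 0.33 through 0.75 to 1.0 under the stated testing assumptions, or above 1 if BioFire cases are tested more completely. A spurious significant difference is unlikely: at most 3.7% of trials for assumed AKI risks up to 20%, but 11% at 30%, so that reassurance is conditional on the risk. The realistic harm is a misleading or falsely reassuring count. The documents do not support a claim that the trial will favour BioFire on renal outcomes, or that the primary comparison is biased; the primary analysis and the sample size are unaffected.

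**What to change.** In section 4.4.2:
1. Report, by arm, how many children had any creatinine and any blood count through follow-up. Do the Day 28 record review for every child whose data are retained (section 4.2.3 lets families withdraw all data).
2. Present AKI and HUS descriptively, as detected cases over all randomized children with retained data, next to the number untested, and not as a rate among tested children only. Best-case and worst-case bounds can be an optional sensitivity analysis.
3. State that a difference in detected counts, in either direction, is not by itself evidence of benefit or harm.
4. Report renal replacement therapy alongside, with exact 95% confidence intervals. It is in section 4.1.1 but missing from the 4.4.2 list, and it does not depend on blood testing in the same direct way. For scale, 0/30 still allows up to 1 − 0.025^(1/30) = 11.6%.

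**Cost.** A few sentences and one table, with no new patients or blood draws. The trial gives up a near-powerless test for AKI and HUS and takes on record review for every child. The bounds will be wide: with 30 per arm and testing at 60% v 20%, 12 and 24 children are untested, so with no detected case they run from 0 to 40% and from 0 to 80%. The plan must also say whether the Bonferroni divisor stays at 8 (0.00625, conservative) or falls to 6 (0.05/6 = 0.0083).

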The **BioFire Gastrointestinal Panel FilmArray®¹⁷** is a multiplexed nucleic acid (NA) based device that simultaneously identifies 22 enteric pathogens. It specifically tests for the presence of Shiga toxin and for O157. It requires 2 minutes of hands-on-time, returns results in ~1 hour, and is Health Canada and Food and Drug Administration approved. The device, which has been validated,¹⁸⁻²¹ hopefully will enable the early identification of infected children and initiation (or withholding) of interventions directed by previously unavailable clinical data. It will enable us to bring a precision medicine approach into ED care. Our proposal is the first attempt to evaluate the ability of this technology to minimize testing and treating to those most likely to benefit. Such an evaluation that is needed by knowledge users to justify integration into care.

Ethics ID: REB17-1916

Title: Improvements Through the Use of a Rapid Multiplex PCR Enteric Pathogen Detection Kit in Children with Hematochezia

PI: [name]

Version 5.0 – May 16, 2018

Previous REB Approved Version Date: January 12, 2018

2 Knowledge Gaps

Each year, in the United States, 31 pathogens cause 9.4 million episodes of foodborne illness, 55,961 hospitalizations, and 1,351 deaths.²² While a small proportion of this overall burden is due to STEC infection, 3% of all children with diarrhea associated HUS die.² In a study that included over 30,000 participants, STEC accounted for 39% of all bacterial pathogens identified²³ and children 5 – 9 years of age were the group with the highest prevalence of STEC infection.²³ We are targeting children with bloody diarrhea as *E. coli* O157:H7 infection is 59 times more common (95% CI, 37 to 96) in visibly bloody stool specimens than in non-bloody specimens.²³ Lastly, this issue is of paramount importance to Southern Alberta as the incidence of diarrhea-associated HUS is two to threefold higher than other parts of Canada, North America and Europe.²⁴

We intend to determine new knowledge:

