Children randomized to the BioFire FilmArray arm will have the same data collected, but stool, if available, will be sent STAT to Calgary Laboratory Services (CLS) for the performance of the BioFire FilmArray test and routine culture. If stool is unavailable, a rectal swab will be performed and sent to CLS for the performance of the BioFire FilmArray test and routine culture. A routine stool specimen for back-up culture will still be requested as per standard of care once it is available. The result of the BioFire test will be printed and brought to the ED where it will be provided to the ED physician for immediate review and management as appropriate. The result will be included in the ED chart for documentation purposes. Education regarding the interpretation of BioFire FilmArray results will have been performed in advance to all faculty members and a research team member will be available to answer any questions should they arise. We have worked with leaders at CLS including Drs. [name], [name] and [name] who believe we should be able to receive a result within 2-3 hours of receipt of the specimen at CLS. Treatment decisions will be at the sole discretion of the ED treating physician who receives the result. Following the completion of the visit, data regarding all testing, procedures, and medications administered will be collected. The family will be contacted 14 days later to collect outcome information (clinical and health resource use) and satisfaction. The medical records and select administrative databases may be reviewed to ascertain and confirm outcome data on Day 28.

All children 6 months – 18 years of age will be eligible for participation (STEC infection is exceedingly rare in children < 6 months of age). Children previously enrolled in the study will be ineligible to participate.

For those who decline consent, we will request consent to access select administrative data, Netcare and/or access to the child's medical records related to the illness to document interventions and outcomes in order to be able to assess bias by comparing participating and non-participating children in this study.

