4.3 Study Procedures

Children randomized to the standard of care arm and the BioFire FilmArray arm will have clinical data collected:

- 1) Day 0 – ED enrollment visit (In person): At the initial screening visit, the research assistant or research nurse will explain the nature of the research project to the family. Informed consent, and assent if applicable, will be obtained. A detailed medical history will be documented to ensure the subject's eligibility for inclusion in the study. Parents will be asked to participate in a standardized 10 minute survey administered by study personnel. The survey will collect descriptive data regarding current medical history (i.e. diarrhea – frequency/duration/blood; vomiting – frequency/duration; fever; pain; health care use; treatment required/procedures performed), previous medical history (i.e. investigations), household pets, and childcare arrangements. The information will be entered in our electronic data capture system (REDCap), and all charts will be reviewed in the ED.
 - a. Specimen Collection: Subjects who qualify for the study will have a stool sample collected, or a rectal swab specimen will be collected if stool is not available for either cohort (Standard Care and BioFire). Children who have a rectal swab collected at this visit will be requested to submit a stool specimen for culture after the ED visit.
 - b. Letter to parents: Only subjects randomized to the BioFire FilmArray arm will be given a letter. The letter outlines their assignment to the BioFire arm and what that means.
- 2) Day 14 Follow-Up: Data regarding ongoing symptoms, any hospital visits/admissions and locations of the respective hospital visits/admissions, testing and procedures conducted as well as parental satisfaction of the experience at the ED will be collected. Parental reports will act as source documentation for data that is related to any additional healthcare visits as well as care in relation to the respective visits not associated with the Alberta Children's Hospital. At the initial point of contact, we will collect the following data: home, cell, work and alternate telephone numbers. For phone follow-up, we will call all numbers provided at least once daily (maximum 5 attempts). Study participants will not be identified by name on study document except the Contact Sheet.

Ethics ID: REB17-1916

Title: Improvements Through the Use of a Rapid Multiplex PCR Enteric Pathogen Detection Kit in Children with Hematochezia

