PI: [name]

Version 5.0 – May 16, 2018

Previous REB Approved Version Date: January 12, 2018

Page 12 of 19

All standardized surveys employed in this study will consist of a series of single-and multiple-select closed-ended items. We will also allow for the selection of a residual “other” category. In cases in which the respondent feels that his or her response does not correspond to one of those already listed (ie. he/she selects “other”), the respondent will be asked to elaborate on his or her answer in full text.

- 3) Day 28: The medical records, Netcare and select administrative databases may be reviewed to ascertain and confirm outcome data on Day 28. This chart review will collect descriptive data regarding subsequent hospital visits and/or subsequent hospital admissions. Variables such as date and time of visit/admission, discharge diagnosis, investigations completed, complications or procedures performed and medications administered will be collected. Chart reviews will serve as source documentation for all data that is related to the Alberta Children’s Hospital.

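### The tree meant to set STEC testing criteria rests on about 6 expected cases with no validation stated, so it can explore criteria but not determine them

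*Combined protocol and SAP*

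**What the plan says.** Secondary Objective 3 (Section 3) reads: "To determine testing criteria to optimize the clinical improvement emerging from use of the BioFire FilmArray (i.e. predictors of bacterial etiology". The matching analysis in 4.4.2 is one sentence. It plans recursive partitioning to find clinical features that "select candidates for BioFire testing that maximize specificity and sensitivity to identify STEC patients". The section gives no predictor list, error weights, pruning rule, case definition, internal validation or interval for the tree.

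Section 2 gives the expected prevalence: "As ~10% of eligible children will have STEC infection". Section 4.4.1 sets the total at 60 from the blood-testing outcome, to be recalculated after 30 children.

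The candidate features come from the Day 0 survey (4.3). It covers diarrhea, vomiting, fever, pain, health care use and treatment, and also "previous medical history (i.e. investigations), household pets, and childcare arrangements". On format, 4.3 says "All standardized surveys employed in this study will consist of a series of single-and multiple-select closed-ended items".

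On STEC status, the standard-care paragraph of 4.1 says "If stool is unavailable a rectal swab will be collected and sent to Calgary Laboratory Services (CLS) for routine culture". In the BioFire arm the specimen is "sent to CLS for the performance of the BioFire FilmArray test and routine culture". Culture is therefore planned in both arms and the PCR panel in one.

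**The concern.** A tree searches many splits and keeps those that fit best. With a handful of cases, some split will separate them from the rest by chance, and accuracy measured on the same children then looks good whether or not any feature is informative. The usual protections are fixed settings, internal validation and a modest claim. 4.4.2 states neither of the first two, and the objective claims to determine criteria.

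At stake is who would be tested. Section 8 foresees working with the laboratory to bring the technology into routine care, and using the data in larger proposals. A rule that only looked accurate could carry into that work. Two ambiguities add to this: the objective and the analysis name different targets, and the definition of an STEC patient is left open when the two arms are tested differently.

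**Working it through.** **1. The plan's own sample size.** Inputs from 4.4.1 and 4.4.2: 60% against 20%, two-sided 5%, Fisher's exact test, 80% power. Exact power is 0.802 with 27 per arm and 0.799 with 26, so 54 reproduces. With 10% loss, 54 / 0.90 = 60. This calculation concerns blood testing only.

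**2. Expected STEC cases.** 60 × 0.10 = 6.0. The 2.5 to 97.5% limits of Binomial(60, 0.10) are 2 and 11, and the chance of 2 or fewer is 5.3%. With 54 children, 54 × 0.10 = 5.4. If only PCR-tested children counted, the 30 tests in the budget (Section 7) would give 30 × 0.10 = 3.0 (range 0 to 7).

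**3. Best-case precision.** If all k cases are detected, the exact 95% lower limit for sensitivity is 0.025^(1/k).
- k = 6: 0.025^(1/6) = 0.541.
- 5 of 6 detected: interval 36% to 99.6%.
- k = 12, as expected if the recalculation doubled N to 120: 0.025^(1/12) = 0.735.

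These limits suppose a rule fixed in advance. A rule chosen on the same cases is less certain still.

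**4. What a tree finds in pure noise.** Simulated trees used 60 children, 6 cases and items unrelated to STEC. The item lists, tree depths and leaf sizes are assumptions, because the plan gives none. The 4.3 survey suggests about 7 symptom features, or 6 if the presence of blood is set aside because every eligible child has it, and up to 12 with history and exposures. In all rows but the last, cases and non-cases carry equal total weight.

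| Setting | Sensitivity | Specificity |
|---|---|---|
| 5 to 20 binary items, depth 2 to 3, leaf 5 to 7, apparent | 78–97% | 59–73% |
| 6 items, split 20, leaf 7, apparent | 85% | 62% |
| 12 items, split 20, leaf 7, apparent | 90% | 67% |
| 10 to 15 items, depth 2 to 3, leaf 5 to 7, five-fold cross-validated | 35–41% | 60–64% |
| Equal cost per misclassified child, leaf 5 to 7 | 0–26% | 98–100% |

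The first row is the range rounded to roughly 80 to 97% elsewhere in this point. As one example, take 10 items, depth 3 and leaf 7. The apparent Youden index is 0.94 + 0.62 − 1 = 0.56, and the cross-validated index is 0.41 + 0.60 − 1 = 0.01. Trees applied to 3,000 new simulated children gave sensitivity + specificity = 1.00, which is no discrimination.

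**5. Pruning.** With cross-validated pruning, a rule survives pure noise in 56 to 58% of runs (minimum error) or 26 to 31% (one-standard-error rule). Survivors still show 89 to 95% apparent sensitivity at 54 to 64% specificity.

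**6. Limits of validation.** With 6 cases, repeated stratified five-fold cross-validation under noise centres on a Youden index of about zero (−0.02 to 0.00). Its SD is 0.22 to 0.24 and its 95th percentile 0.43. Cross-validation removes the bias but not the imprecision.

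**7. Targets side by side.** Section 3 names predictors of bacterial etiology; 4.4.2 names STEC patients. STEC is one bacterial pathogen among several on the panel, so these are different outcomes with different case counts.

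**The case against.** The strongest reply is that the damage depends on choices the plan does not make. It does not say that apparent accuracy will be reported, that the classes will be weighted equally, or that the tree will go unpruned. This stands in part. A reader might infer that the plan will produce a false rule, and the documents do not support that. With equal cost per misclassified child a tree on this many cases labels almost nobody positive, and the one-standard-error rule removes most noise trees. Equal class weighting is an inference, though a natural one: the per-child version has almost no sensitivity, contrary to the stated aim. The limit of 54% for 6 of 6 needs none of these assumptions.

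A reader might also take a single setting as the expected size. For example, 7 to 12 items with split 20 and leaf 7 give 88 to 94% at 62 to 70% when some items have four levels. Other stopping rules gave 81 to 100% at 48 to 79%, and with seven correlated items sensitivity fell to 83 to 85%. Only a wide, conditional range is defensible.

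A third tempting step uses "STEC accounted for 39% of all bacterial pathogens identified" to compute 60 × 0.10 / 0.39 = 15.4 bacterial cases. That share comes from a study of over 30,000 participants, not from children selected for bloody diarrhea. The same section says that E. coli O157:H7 is 59 times more common in visibly bloody specimens, so the share need not transfer. The mismatch of targets stands; the figure of 15 does not.

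Finally, it might seem that culture must be the reference because both arms have it. The documents do not settle this. The tree selects children for BioFire testing, so treating PCR-only positives as non-cases is debatable.

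**Conclusion.** The point holds for a secondary objective. About 6 STEC cases (95% range 2 to 11) cannot determine testing criteria: perfect detection of all 6 would still leave sensitivities down to 54% compatible with the data. This rests only on N = 60 and the protocol's 10% prevalence.

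The risk of a misleading rule is conditional. If cases and non-cases are weighted equally and apparent accuracy is reported, uninformative items can show roughly 80 to 97% sensitivity at 59 to 73% specificity, depending on item number, tree size and pruning, all of which are assumed. The plan neither commits to that course nor rules it out.

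The mismatch between bacterial etiology and STEC, and the undefined STEC case, are plain from the text. The primary comparison of blood testing is unaffected.

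**What to change.** **Secondary Objective 3.** Change the verb so that the aim is to explore candidate testing criteria. Name the same target there and in 4.4.2: STEC, bacterial etiology, or both as separate trees.

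**Section 4.4.2.** Replace the sentence on recursive partitioning with a paragraph stating that:
- the analysis is exploratory and hypothesis-generating;
- a short list of Day 0 predictors, the class weights and the pruning rule are fixed before analysis;
- sensitivity and specificity come from repeated stratified cross-validation that repeats every tree-building step, including pruning, in each fold;
- they are reported with the number of cases and a statement that uncertainty is wide;
- apparent accuracy is not reported as performance;
- any criteria need validation in other data.

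**Case definition.** State one definition applied in the same way to both arms, because PCR is done in one arm only. The choice of definition, and of any minimum number of cases for fitting a tree, is the sponsor's. A short predictor list alone is not enough: with four noise items, apparent accuracy was still 81 to 88% at 58 to 62%.

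**Cost.** One paragraph and one phrase in a short amendment, with no new data. Objective 3 becomes exploratory, and the reported accuracy will look less favourable.
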